10.1.1.2 Injection-training Visit at Screening (Visit 2/Week -1/Day -7 ± 7)

- Assess inclusion/exclusion criteria
- Collect AEs
- Record concomitant medication
- Take vital signs including HR and BP
- IVRS/IWRS contact for allocation of a batch number for training kit
- Record batch number allocated in e-CRF
- Injection training should be provided as outlined in [Section 8.1](#)
- The placebo for alirocumab should be administered by the patient or another designated person (such as spouse, relative, etc) at the study site under supervision of site staff with appropriate feedback
- If patient will undergo the second optional injection training with placebo for alirocumab, then the following steps are needed. However, if patient does not need a second optional training injection with placebo then do not perform these steps:
 - Recontact IVRS/IWRS for allocation of a second new batch number for a second training kit
 - Record the second batch number allocated in e-CRF
 - Dispense the second placebo training injection to the patient for self-administration

- An appointment will be given for the next visit
- Remind patient to be in fasting conditions (ie, overnight, at least 10 to 12 hours fast and refrain from smoking) for next visit. Also, alcohol consumption within 48 hours and intense physical exercise within 24 hours preceding the next visit are discouraged

10.1.2 Double-Blind Double-Dummy Treatment Period (Study Site Visits)

10.1.2.1 Randomization Visit (Visit 3/Week 0/Day 1 + 3)

- Assess Inclusion/Exclusion Criteria
- Collect AEs
- Record concomitant medication
- Review patient's diet. Patient should be on a NCEP ATP III TLC diet or equivalent.
- Perform physical examination
- Get body weight measurement
- Take vital signs including HR and BP
- [REDACTED]
- [REDACTED]
- Present ICF for the optional PK (for a subset of patients), and if patient agrees to participate then obtain written consent.
 - If patient declines participation in the PK then this has no consequences for participation in the study otherwise.
- Urinalysis
- Urine pregnancy test (WOCBP only).
- Obtain fasting blood sample for:
 - Lipids: measure and/or calculation of TC, LDL-C, HDL-C, TG, non-HDL-C, Apo B, Apo A-1, Apo B/Apo A-1 ratio and Lp(a)
 - Library samples
 - Hematology: CBC including RDW and reticulocyte count, hematocrit, Hb, red blood cell count, white blood cell count with differential blood count and platelet
 - Chemistry: glucose, sodium, potassium, chloride, bicarbonate, calcium, phosphorous, urea nitrogen, creatinine, uric acid, LDH, total protein, albumin and γ GT
 - Liver panel (ALT, AST, ALP, and total bilirubin)
 - CPK

- Anti-alirocumab antibodies (to be performed prior to the IMP injection, after randomization)
- Serum alirocumab concentration (PK), for specifically consented patients only (to be performed prior to the IMP injection, after randomization)
- [REDACTED]
- If the patient is confirmed eligible (and in fasting conditions), the Investigator will start the next study procedures:
 - IVRS/IWRS contact for randomization and allocation of two 7-digit treatment kit numbers according to the randomization list, for the alirocumab injections and the ezetimibe capsules. Investigators should never allocate a treatment kit number to a patient without contacting IVRS/IWRS.
- Double-blind IMP kits dispensation as per treatment kit numbers provided by IVRS/IWRS along with schedule reminder. The patient injection instruction manual and treatment administration package should be provided. The patient diary should be given and instructions on its completion should be reviewed.
- The first double-blind IMP injection and the first ezetimibe capsule administration will take place at the study site, but only after the collection of the fasting blood samples and after the assessment of all evaluations planned at that visit. Close supervision, feedback and further training to be provided for IMP administration. The patient should be observed for at least 30 minutes after the injection.
- Reminders
 - An appointment will be given for the next study site visit.
 - Remind patient to be in fasting conditions (ie, overnight, at least 10 to 12 hours fast and refrain from smoking) for next study site visit. Also, alcohol consumption within 48 hours and intense physical exercise within 24 hours preceding the next study site visit are discouraged.
 - Patient to bring the diary, at the next study site visit.
 - Patient to bring used and unused kits at the next study site visit

10.1.2.2 Visit 4/ Week 4, Visit 5/ Week 8 and Visit 7/Week 16 (Day 29, 57 and 113 ± 7)

- Collect AEs
- Record concomitant medication
- Take vital signs including HR and BP
- Data collection on IMP administration and IMP compliance check by review of diary and treatment kit
- Obtain fasting blood sample for:
 - Lipids: measure or calculation of TC, LDL-C, HDL-C, TG, non-HDL-C
NOTE – For Week 8 visit, please ensure that unscheduled fasting blood sample through the Central Lab for the lipid parameters are obtained if the lipid lab parameters

are not done as per schedule or the lipid labs were drawn but an issue is later discovered with the samples which require retesting.

- Liver panel (ALT, AST, ALP, and total bilirubin)
- Anti-alirocumab antibodies (Visit 4/Week 4 only) (to be performed prior to the IMP injection)
- Library sample (Visit 4/Week 4 only)
- Serum alirocumab concentration (Visit 4/Week 4 and Visit 7/Week 16 only), for specifically consented patients only
- Reminders
 - An appointment will be given for the next study site visit.
 - Remind patient to be in fasting conditions (ie, overnight, at least 10 to 12 hours fast and refrain from smoking) for next study site visit. Also, alcohol consumption within 48 hours and intense physical exercise within 24 hours preceding the next study site visit are discouraged.
 - Patient to bring the diary at the next study site visit.
 - Patient to bring used and unused kits at the next study site visit

10.1.2.3 Visit 6/Week 12 (Day 85 ± 3):

- Collect AEs
- Record concomitant medication
- Get body weight measurement
- Take vital signs including HR and BP
- Review patient's diet. Patient should be on a NCEP-ATPIII TLC diet or equivalent
- Urinalysis
- Urine pregnancy test (WOCBP only).
- Obtain fasting blood sample for:
 - Lipids: measure and/or calculation of TC, LDL-C, HDL-C, TG, non-HDL-C, Apo B, Apo A-1, Apo B/Apo A-1 ratio and Lp(a)
 - Library samples
 - Serum alirocumab concentration (PK), for specifically consented patients only
 - Hematology: : CBC including RDW and reticulocyte count, hematocrit, Hb, red blood cell count, white blood cell count with differential blood count and platelet
 - Chemistry: glucose, sodium, potassium, chloride, bicarbonate, calcium, phosphorous, urea nitrogen, creatinine, uric acid, LDH, total protein, albumin and γ GT
 - HbA1c
 - Liver panel (ALT, AST, ALP, and total bilirubin)

- CPK
- Anti-alirocumab antibodies (to be performed prior to the IMP injection)
- Data collection on IMP administration and IMP compliance check by review of diary and treatment kit accountability.
- IVRS/IWRS contact to get treatment kit number for two kits resupply, for the alirocumab injections and the ezetimibe capsules.
- Double-blind IMP kits dispensation as per treatment kit numbers provided by IVRS/IWRS along with schedule reminder and the treatment administration package should be provided. The patient injection instruction manual and diary may be given, as needed.
- Reminders
 - An appointment will be given for the next study site visit.
 - Remind patient to be in fasting conditions (ie, overnight, at least 10 to 12 hours fast and refrain from smoking) for next study site visit. Alcohol consumption within 48 hours and intense physical exercise within 24 hours preceding the next study site visit are discouraged.
 - Patient to bring the diary at the next study site visit.
 - Patient to bring used and unused kits at the next study site visit

10.1.2.4 Unscheduled PK visit / 5 days (± 2) after Week 22 IMP injection or after (optional)

- Obtain fasting blood sample 5 days (± 2 days) after the IMP injection for:
 - Serum alirocumab concentration (PK)

10.1.2.5 Visit 8/Week 24 (Day 169 ± 3): End of treatment visit

- Collect AEs
- Record concomitant medication
- Get body weight measurement
- Take vital signs including HR and BP
- Review patient's diet. Patient should be on a NECP-ATP III TLC diet or equivalent
- Perform 12-lead ECG
- Perform physical examination
- IVRS/IWRS contact to document the end of treatment
- Data collection on IMP administration and IMP compliance check by review of diary and treatment kit accountability.
- Urinalysis
- Urine pregnancy test (WOCBP only).

- Obtain fasting blood sample for:
 - Anti-alirocumab antibodies (to be performed prior to the IMP injection).
 - Lipids: measure and/or calculation of TC, LDL-C, HDL-C, TG, non-HDL-C, Apo B, Apo A-1, Apo B/Apo A-1 ratio and Lp(a)
 - Library samples
 - Hematology: CBC including RDW and reticulocyte count, hematocrit, Hb, red blood cell count, white blood cell count with differential blood count and platelet
 - Chemistry: glucose, sodium, potassium, chloride, bicarbonate, calcium, phosphorous, urea nitrogen, creatinine, uric acid, LDH, total protein, albumin and γ GT
 - Hepatitis C Antibody Test (with automatic confirmatory testing if positive)
 - HbA1c
 - Liver panel (ALT, AST, ALP, and total bilirubin)
 - CPK
 - Serum alirocumab concentration (PK)
- Reminders
 - An appointment will be given for the next study site visit.
 - Remind patient to be in fasting conditions (ie, overnight, at least 10-12 hours fast and refrain from smoking) for next study site visit, if needed. Also, alcohol consumption within 48 hours and intense physical exercise within 24 hours preceding the next study site visit are discouraged.
 - Sharp-container (containing all used auto-injectors) must be returned at site for destruction.

10.1.3 Follow-Up Period

10.1.3.1 Follow-Up Visit (Visit 9/ Week 32/ Day 225 \pm 7)

- Collect AEs
- Record concomitant medication
- Get body weight measurement
- Take vital signs including HR and BP.
- Perform physical examination (only in case of clinically relevant abnormality at the end of treatment visit)
- IVRS/IWRS contact to document the end of study
- Urinalysis (only in case of clinically relevant abnormal value at the end of treatment visit)
- Urine pregnancy test (WOCBP only)
- Obtain fasting blood sample for:

- Anti-alirocumab antibodies (as per schedule note in study flowchart of [Section 1.2](#))
- Only in case of clinically relevant abnormal values for these parameters at the end of treatment visit will the following be obtained at this visit:
 - a) Hematology: CBC including RDW and reticulocyte count, hematocrit, Hb, red blood cell count, white blood cell count with differential blood count and platelet
 - b) Chemistry: glucose, sodium, potassium, chloride, bicarbonate, calcium, phosphorous, urea nitrogen, creatinine, uric acid, LDH, total protein, albumin and γ GT
 - c) HbA1c
 - d) Liver panel (ALT, AST, ALP, and total bilirubin)
 - e) CPK

10.2 DEFINITION OF SOURCE DATA

Evaluations that are reported in the e-CRF must be supported by appropriately signed identified source documentation related but not limited to the following:

- Agreement, date, and signature of informed consent mentioning the study identification.
- Patient identification, last participation in a clinical trial, medical history, associated diseases, and data related to the studied pathology.
- Contraception methods for women of childbearing potential.
- Previous and concomitant medication (including the LMT).
- Study identification.
- Treatment number, dates of administration.
- Dates of visits and assessments including the examination report.
- Vital signs, height, body weight.
- Faxed central lab reports (dated and signed by the Principal Investigator or Subinvestigator).
- IVRS/IWRS confirmation fax (screening, screen failure, training kit allocation, randomization, treatment reallocation, discontinuation, end of DBTP, end of study, unblinding if applicable).
- ECG records signed and dated.
- AEs and follow-up:
 - In case of SAE, the site should file in the source document at least copies of the hospitalization reports and any relevant examination reports documenting the follow-up of the SAE.
- Date of premature study discontinuation (if any) and reason.

Source documentation may be found in the following:

- Patient's identity.
- Medical history.
- Hospital records.
- Nursing notes.
- Physician's notes.

10.3 HANDLING OF PATIENT TEMPORARY OR PERMANENT TREATMENT DISCONTINUATION AND OF PATIENT STUDY DISCONTINUATION

The IMP should be continued whenever possible. In case the IMP is stopped, it should be determined if the stop can be made temporarily; permanent IMP discontinuation should be a last resort. Any IMP discontinuation should be fully documented in the e-CRF and source notes. In any case, the patient should remain in the study as long as possible.

Pregnancy will lead to definitive treatment discontinuation in all cases.

10.3.1 Temporary treatment discontinuation with investigational medicinal product(s)

Temporary treatment discontinuation (also referred to as treatment interruption) may be considered by the Investigator because of suspected AEs. Reinitiating of treatment with the IMP will be done under close and appropriate clinical and/or laboratory monitoring once the Investigator will have considered according to his/her best medical judgment that the responsibility of the IMP in the occurrence of the concerned event was unlikely and if the selection criteria for the study are still met (refer to [Section 7.1](#) and [Section 7.2](#)).

All treatment interruption duration should be recorded by the Investigator in the appropriate e-CRF screens when considered as confirmed.

Treatment interruption is defined as one or more scheduled injections or one or more capsules that are not administered to the patient as decided by the Investigator.

10.3.2 Permanent treatment discontinuation with investigational medicinal product(s)

Permanent treatment discontinuation (also referred to as treatment discontinuation) is any treatment discontinuation associated with the definitive decision from the Investigator or the patient not to re-expose the patient to the IMP at any time.

Patient withdrawal from the study treatment or study should be avoided as much as possible.

10.3.3 List of criteria for permanent treatment discontinuation

The patients may withdraw from treatment if they decide to do so, at any time and irrespective of the reason, or this may be the Investigator's decision. All efforts should be made to document the reasons for treatment discontinuation and this should be documented in the e-CRF.

Patients should discontinue the IMP for the following reasons:

- Pregnancy, intention for pregnancy, or no longer with effective contraceptive method of birth control (females only).
- Acute injection reaction of clinical concern.
- Serious adverse event (or non-serious but severe in intensity) of hypersensitivity reaction considered related to IMP.
- At patient request "i.e., withdrawal of the consent for treatment"
- If, in the investigator's opinion, continuation with the administration of the IMP would be detrimental to the patient's well-being.
- Intercurrent condition that requires discontinuation of the IMP (eg, laboratory abnormalities, please refer to decision tree [Appendix D](#)).
- At the specific request of the Sponsor.
- Any code breaking requested by the Investigator.
- Patient receives double-blind treatment prior to randomization

10.3.4 Handling of patients after permanent treatment discontinuation

Patients who prematurely discontinue study treatment (regardless of the reason) should still continue the study and undergo all visits and procedures as described in [Section 1.2](#) with the exception of study treatment administration and its associated procedures. At the time of treatment discontinuation, the patient should have, as soon as possible, an unscheduled visit with assessments normally planned at end of treatment visit (this should take place within 5 days of treatment discontinuation, if possible) and then resume the original study schedule until end of study (ie, follow up visit). In particular, in case of early treatment discontinuation before week 24, all efforts should be done to perform the week 12 and week 24 visits.

If after treatment discontinuation, the patient refuses to continue the study, then if possible, the patient should undergo an unscheduled visit with assessments normally planned at the end of treatment visit (it should take place within 5 days of treatment discontinuation, if possible). The patient, at a minimum, should then be followed up for at least 10 weeks from last study treatment administration or up to recovery or stabilization of any AE to be followed-up as specified in this protocol, whichever comes last. A final end of study visit can take place with assessments as specified in the end of study visit (ie, follow up visit) at 10 weeks after the premature treatment discontinuation.

All definitive discontinuation of study treatment should be recorded by the Investigator in the appropriate screens of the e-CRF and in the patient's medical records when considered as confirmed. IVRS/IWRS should be notified when a patient prematurely discontinues study treatment.

For patients randomized and not treated, all efforts should be made to perform the Week 12 and Week 24 visits in order to collect the laboratory data and at the least, the lipid parameters.

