9 ASSESSMENT OF INVESTIGATIONAL MEDICINAL PRODUCT

9.1 EFFICACY ENDPOINTS

9.1.1 Primary efficacy endpoint

The primary efficacy endpoint is the percent change in calculated LDL-C from baseline to Week 24, in the intent-to-treat (ITT) population, using all LDL-C values regardless of adherence to treatment (ITT estimand). Primary endpoint is defined as:
$$100 \times (\text{calculated LDL-C value at Week 24} - \text{calculated LDL-C value at baseline}) / \text{calculated LDL-C value at baseline}$$

The baseline calculated LDL-C value will be the last LDL-C level obtained before the first double-blind IMP defined as the earliest between the first double-blind injection and the first capsule intake.

The calculated LDL-C at Week 24 will be the LDL-C level obtained within the Week 24 analysis window.

All calculated LDL-C values (scheduled or unscheduled, fasting or not fasting) may be used to provide a value for the primary efficacy endpoint if appropriate according to above definition. The analysis window used to allocate a time point to a measurement will be defined in the Statistical Analysis Plan (SAP).

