9.1.3 Efficacy assessment method

9.1.3.1 *Lipid parameters*

Total cholesterol, HDL-C, TG, Apo B, Apo A-1, and Lp(a) will be directly measured by the Central Laboratory as per the schedule in [Section 1.2](#). LDL-C will be calculated using the Friedewald formula [\(17\)](#) at all visits (except Week -1 and Follow Up visit). If TG values exceed 400 mg/dL (4.52 mmol/L) then the central lab will reflexively measure (via the beta quantification method) the LDL-C rather than calculating it. LDL-C will also be measured (via the beta quantification method) at Week 0 and Week 24. Non-HDL-C will be calculated by subtracting HDL-C from the TC. Apo B/Apo A-1 ratio will be calculated. Detailed procedures of sample preparation, storage and shipment will be described in the specific laboratory manual which will be provided to sites. Information on the processing, methodology and other relevant information will be available in the Reference Laboratory Manual.

Efficacy endpoints will not be considered as AEs, such as those involving abnormalities in lipid levels, unless meeting the criteria in [Section 10.4.3](#).

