## Appendix B Detailed statistical methodology for pattern mixture model

As a sensitivity analysis of the primary efficacy endpoint (i.e. percent change from baseline to Week 24 in calculated LDL-C), a pattern-mixture model approach will be used, with a different imputation strategy applied for missing calculated LDL-C values during the on-treatment period (ie, within the time period from the first double-blind IMP injection up to the day of the last injection +21 days) and missing calculated LDL-C values after treatment discontinuation (ie, after the day of last injection +21 days) based on the following assumptions:

- Patients within 21 days of their last IMP injection would continue to show benefit from treatment similar to that observed at the scheduled time point. Therefore, calculated LDL-C values missing during the on-treatment period will be considered “Missing At Random” and imputed using a model estimated using all samples collected on treatment.
- Patients who stopped taking their study treatment no longer benefited from it in the future, and thus tended to have calculated LDL-C values returning to baseline. Thus calculated LDL-C values missing after treatment discontinuation will be imputed based on patient’s own baseline value.

The assumptions for this approach are based on the following considerations:

- Missing values during the on-treatment period are mostly consecutive to:
  - Visits performed outside of the pre-specified time-window
  - No blood sample available although visit was done
  - Calculated LDL-C not measurable due to technical reasons

In addition, these missing data are often intermittent, i.e. followed by calculated LDL-C values collected at subsequent visits. It is therefore considered reasonable to assume that these missing data were “At Random”.

- Phase 2 studies DFI11565 and R727-CL-1003 included a prospective assessment of calculated LDL-C during the follow-up period after a 12-week treatment period. These studies showed that after treatment discontinuation, the average calculated LDL-C returned to baseline level within 4 weeks after ceasing alirocumab treatment.

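### Patients who stop drug and leave but attend the optional 10-week final visit have no lipids drawn there, so off-drug LDL-C values inside the Week 12, 16 or 24 windows go uncollected (low severity)

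*Protocol*

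**What the plan says.** Protocol 10.3.4 has two routes after permanent discontinuation of study drug.

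- **Patients who stay in the study** keep every scheduled visit, with particular effort asked for Weeks 12 and 24. Their off-drug lipids are collected.
- **Patients who decline to go on** are covered separately: "If after treatment discontinuation, the patient refuses to continue the study, then if possible, the patient should undergo an unscheduled visit". That early visit repeats the end-of-treatment procedures, lipids included, ideally no later than 5 days after stopping. They "should then be followed up for at least 10 weeks from last study treatment administration". The last contact is described as follows: "A final end of study visit can take place with assessments as specified in the end of study visit (ie, follow up visit", timed "at 10 weeks after the premature treatment discontinuation".

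The follow-up visit carries no lipids. The flow chart (Protocol 1.2) has no lipid mark at Week 32. The visit list in Protocol 10.1.3.1 has a fasting blood draw for antibodies, plus safety tests only where the end-of-treatment result was abnormal. Protocol 9.1.3.1 provides for calculated LDL-C "at all visits (except Week -1 and Follow Up visit". The follow-up window in SAP Table 2 is for antibodies and vital signs only.

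The primary endpoint is analysed "using all LDL-C values regardless of adherence to treatment (ITT estimand". Protocol 9.1.1 and SAP 2.1.3 accept unscheduled values if they fall in a window. SAP 2.4.4.1.1 handles missing values by MMRM and acknowledges that this rests on missing at random. SAP Appendix B reports, from two phase 2 studies, that "the average calculated LDL-C returned to baseline level within 4 weeks after ceasing alirocumab treatment".

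**The concern.** The estimand asks what LDL-C is at Week 24 whether or not the patient is still on drug. For a patient who stops and leaves, the early visit comes within about 5 days of stopping, while the drug effect is still largely present. The 10-week visit is the only contact at which the off-drug level could be seen, and fasting blood is already planned there. If it falls inside an efficacy window, the value the estimand needs could be observed but is not.

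The MMRM then has only values at or near on-drug level for these patients and predicts Week 24 accordingly, while the SAP's own evidence for alirocumab says LDL-C is back at baseline well before 10 weeks. The expected on-drug effect is larger for alirocumab than for ezetimibe, so the error favours alirocumab.

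**Working it through.** **1. The plan's own figure.** Protocol 11.1 gives 96 patients (64 and 32) for 95% power, with a difference of 20 points, SD 25 and two-sided 0.05. A two-sample t-test gives 95.5% power at 64:32 and 94.9% at 62:31, so 96 is the smallest 2:1 total that reaches 95%. The figure is reproduced. This point does not depend on it, but the SD and the difference serve as yardsticks below.

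**2. When the final visit falls.** Final visit day = stop day + 70, compared with SAP Table 2.

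| Stop day | Final visit day | Analysis window |
|---|---|---|
| 1–28 | 71–98 | Week 12 |
| 29–56 | 99–126 | Week 16 |
| 57–84 | 127–154 | none |
| 85–112 | 155–182 | Week 24 |
| 113 or later | 183 or later | none |

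- Table 2 can close the Week 12 window early, at the first injection from the kit allocated at up-titration. A patient who stopped by Day 28 has no such injection, so the limit of Day 98 stands.
- With the ±7-day visit tolerance, stops on Day 78 to 119 could land in the Week 24 window. Stops on Day 92 to 105 do so wherever in the tolerance the visit falls.
- Section 10.3.4 anchors the 10 weeks once on the last administration and once on discontinuation, which moves these bands slightly.

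**3. Whether another Week 24 value exists.** For stops on Day 85 to 112 the early visit falls on Day 85 to 117 (112 + 5). The Week 24 window opens on Day 155, so no Week 24 value remains.

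**4. How many values.** The documents give no rate for patients who stop, leave and still attend. Assume 12 to 60 of 600 (2% to 10%), with stop days spread evenly over Day 1 to 168.

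- Week 24: 28/168 = 16.7%, so 2 to 10 values.
- Week 12 or 16: 56/168 = 33.3%, so 4 to 20 values.

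**5. Effect on the primary comparison.** Let L be the number of lost Week 24 values, split 2:1 between arms. Assume the true off-drug change is about 0, and that the model predicts the full on-drug mean: −50% for alirocumab and −25% to −30% for ezetimibe (Protocol section 4).

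- Alirocumab arm: (L × 2/3)/400 × 50. This is 0.17 points at L = 2 and 0.83 at L = 10.
- Ezetimibe arm: (L × 1/3)/200 × (25 to 30). This is 0.08 to 0.10 at L = 2 and 0.42 to 0.50 at L = 10.
- Treatment difference: L/600 × (20 to 25). This is 0.07 to 0.08 at L = 2 and 0.33 to 0.42 at L = 10.

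The return-to-baseline evidence in Appendix B is for alirocumab. If the ezetimibe arm did not shift at all, the overstatement would be the alirocumab figure alone, 0.17 to 0.83 points.

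**6. Yardstick.** The standard error of the difference is 25 × √(1/400 + 1/200) = 2.17 points. The overstatement of 0.07 to 0.42 is about 3% to 19% of one standard error. The planned 20 points is about 9 standard errors.

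**The case against.** The strongest reply is that this is a consistent design rather than a mistake. Every relevant place leaves lipids out of follow-up, and that visit exists for safety while residual drug clears. Section 10.3.4 first tries to keep all patients on the full schedule, so someone willing to come in fasting around Day 169 could simply be offered the Week 24 visit. An unscheduled central-laboratory sample is not forbidden and would be analysed. The pattern-mixture analysis already imputes values missing more than 21 days after the last injection around the patient's own baseline, which is what the lost sample would be expected to show. The effect is a small fraction of a standard error.

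Most of this stands. A reader might infer that the protocol contradicts itself, or that stopping drug in itself costs the Week 24 value. The documents support neither: the omission is uniform, and patients who stay keep their lipid visits. Nor are the two leaver visits guaranteed, since one is to be held only if possible and the other is worded as something that can take place.

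Three things remain. Nothing tells the site to take the sample, and the visit list points the other way. Local lipid testing is barred after randomization except for patient safety (Protocol 6.1), so there is no substitute. The pattern-mixture model is a sensitivity analysis that draws an assumed value, with cited support for alirocumab only. It does not recover an obtainable observation. Section 10.3.4 itself asks for lipids, at the least, from patients randomized but never treated; leavers who still attend the final visit have no equivalent clause.

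**Conclusion.** The gap is real and narrow. It concerns patients who stop drug, refuse the remaining schedule and still attend the optional 10-week visit, when that visit falls in the Week 12, 16 or 24 window. For them an off-drug LDL-C value that the ITT estimand would use is not drawn, and the primary MMRM relies on missing at random from values at or near on-drug level.

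Under the stated assumptions (2 to 10 lost Week 24 values, evenly spread stop days, full on-drug prediction, return to baseline in both arms) the treatment difference is overstated by about 0.07 to 0.4 points in favour of alirocumab. The number of patients is assumed, not documented.

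A reader might infer that the primary result is at risk. It is not: even the larger figure for a shift in the alirocumab arm alone, 0.83 points, is below 0.4 of a standard error, and the pattern-mixture analysis partly covers the mechanism. This is a low-severity improvement to data collection.

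**What to change.** In Protocol 10.3.4, state that, if the patient agrees, a fasting lipid panel (TC, HDL-C, TG, calculated LDL-C, non-HDL-C) goes to the central laboratory from this final visit when it falls on Day 71–98, 99–126 or 155–182. Add Apo B, Apo A-1 and Lp(a) in the Week 12 and Week 24 windows, where their changes are key secondary endpoints. Results stay masked.

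Tying the sample to the windows avoids drawing blood that the window-based analyses would not use, as on Day 127–154. Agreement matters because Protocol 10.3.5 separates consent for treatment from consent for follow-up visits.

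Align the flow chart in 1.2 and sections 9.1.3.1 and 10.1.3.1 so that they do not contradict the new sentence. The SAP needs no change, because 2.1.3 already assigns unscheduled central-laboratory values to the analysis windows.

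The cost is a short wording change in four places, a small laboratory charge, and one extra tube for a few patients at a visit where fasting blood is already planned.
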